## 3.5. Safety Endpoints

The following data are considered in standard safety summaries (see protocol for collection days and list of parameters):

- AEs,
- laboratory data,
- vital signs data,
- ECG results.

# **Adverse Events**

For SAEs, the reporting period to Pfizer or its designated representative begins from the time that the subject provides informed consent, which is obtained prior to the subject's participation in the study, ie, prior to undergoing any study-related procedure and/or receiving IP, through and including 28 calendar days after the last administration of the IP.

Similarly, the time period for collecting AEs ("active collection period") for each subject begins from the time the subject provides informed consent. The AEs occurring following start of the double-blind randomized treatment will be counted as treatment-emergent. The AEs occurring prior to the double-blind randomized treatment intake will be listed.

The 3-Tier approach will not be used to summarize the AEs due to the small sample size.

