6. STUDY PROCEDURES

A signed and dated Informed Consent Document (ICD) will be obtained from each subject at Visit 1 (Screen 1) before performing any protocol-specific procedures. All requirements and procedures of the trial will be thoroughly reviewed with all subjects. The results of the clinical laboratory assessments and all screening procedures will be evaluated with respect to inclusion and exclusion criteria to determine the subject's eligibility. If a subject does not qualify for the trial, he or she will be considered a screen failure. Adverse Event (AE) reporting, including Serious Adverse Event (SAE) reporting will begin from the time the ICD is signed at Visit 1 (Screen 1).

For the procedures described below, where multiple procedures are scheduled at the same time points relative to dosing, the following chronology of events should be adhered to as much as possible:

- *12-lead ECG*: obtain prior to vital signs assessment, blood samples, and prior to dosing;
- *Vital Signs (BP, pulse rate)*: obtain after 12-lead ECG collection but prior to obtaining blood samples and prior to dosing;
- *Fasting blood samples, including pre-dose PK*: after assessment of 12-lead ECG and vital signs but prior to dosing;
- *Other pre-dose procedures*: should be obtained/performed as close as possible to the scheduled time, but may be obtained before or after blood specimen collection;
- *Dosing of blinded IP(s)*: must occur after any pre-dose blood sample collections.

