6.1. Screening

Refer to the Schedule of Activities for the study procedures to be completed at the Screening visits. The 3 screening visits are to be performed sequentially.

- At Screen 1, subjects will be consented and all screening procedures (except liver fat assessment by 2nd FibroScan and by MRI-PDFF) undertaken to determine eligibility refer to Section 4.1 and Section 4.2;
- Only after subjects are identified to be otherwise eligible, should they proceed with Screen 2 for another FibroScan[®] assessment as performed at Screen 1;
- Following confirmation of liver fat content at Screen 2, subjects should proceed to the Imaging center for the Screen 3 visit to undergo liver fat assessment via MRI-PDFF acquisition to assess whether they meet inclusion criterion 8, Section 4.1.

For Visit 1, subjects will be instructed to arrive at the study site after at least an 8-hour, but preferably 10-hour fast (except water). For Visits 2 and 3, fasting (water allowed) for \geq 4 hours is required.

Subjects will be screened **within56 days** (including 14 days of single-blind Run-In period) prior to the first dose of the blinded IP to confirm that they meet the subject selection criteria for the study. The duration between Screen 1 (Visit 1) and start of Run-In period (Visit 4) should be **at least 28 days**, but should not exceed 42 days. In rare cases, subjects may be re-screened; however, this is permitted only when, due to logistical constraints, the maximum period between the Screen 1 and Day 1 of **72 days** is exceeded. In such cases, all screening procedures must be repeated and the subject assigned a new 8-digit single subject identifier (SSID) number. Subjects must be deemed to meet all the eligibility criteria including assessment of liver fat via MRI-PDFF at Screen 3, under the new 8-digit SSID.

To prepare for study participation, subjects will be instructed on the use of Lifestyle Requirements (Section 4.4) and Concomitant Treatments (Section 5.8).

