8.3. Severity Assessment

If required on the AE page of the CRF, the investigator will use the adjectives MILD, MODERATE, or SEVERE to describe the maximum intensity of the AE. For purposes of consistency, these intensity grades are defined as follows:

Severity Assessment		
MILD	Does not interfere with subject's usual function.	
MODERATE	Interferes to some extent with subject's usual function.	
SEVERE	Interferes significantly with subject's usual function.	

Note the distinction between the severity and the seriousness of an AE. A severe event is not necessarily an SAE. For example, a headache may be severe (interferes significantly with the subject's usual function) but would not be classified as serious unless it met one of the criteria for SAEs, listed above.

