# **Adverse Events**

Adverse events will be summarized by treatment and in accordance with current Pfizer data standards. The AEs will be sorted alphabetically within a system organ class. Summary tables will be provided for treatment-emergent adverse events (TEAEs) and AEs occurring prior to randomization will only be listed.

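### The SAP's definition of a treatment-emergent AE has no worsening clause, so an AE ongoing at Day 1 that worsens on drug may be listed but left out of the by-arm tables

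*SAP*

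**What the plan says.** SAP Section 3.5 (Adverse Events) divides AEs at the start of double-blind dosing. On one side, "The AEs occurring following start of the double-blind randomized treatment will be counted as treatment-emergent". On the other, "The AEs occurring prior to the double-blind randomized treatment intake will be listed".

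SAP Section 6.6 (Adverse Events) carries the split into the outputs: "Summary tables will be provided for treatment-emergent adverse events (TEAEs) and AEs occurring prior to randomization will only be listed". The same paragraph opens with a reference to an outside standard: "Adverse events will be summarized by treatment and in accordance with current Pfizer data standards".

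The protocol uses the term treatment-emergent in its secondary endpoint (Section 2) but does not define it. AE collection starts at consent at Screen 1 (Protocol Sections 6 and 8.1.4), so AEs accrue through screening and the placebo run-in. Where the CRF asks for severity, Protocol Section 8.3 has the investigator use mild, moderate or severe "to describe the maximum intensity of the AE". No section tells sites whether an ongoing AE that worsens stays as one record or becomes a new one.

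**The concern.** A safety comparison should capture harm that begins on drug and also harm that drug makes worse. The SAP's split deals with the first and is silent on the second. Take a headache that starts in run-in as mild and becomes severe in week 2 of dosing. Kept as one record, it has a pre-dose start and a maximum grade of severe. Under the split it belongs with the earlier events, which SAP Section 6.6 sends to a listing.

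Treatment-emergent AEs are part of the secondary endpoint, and the secondary objective compares the combination with placebo and with each monotherapy. Symptomatic complaints matter most here, because no laboratory, vital-sign or ECG table would show their worsening by arm. If a regimen aggravates existing complaints more than its comparator does, the AE tables would understate that difference.

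**Working it through.** **1. How long AEs can accrue before dosing.** Inputs: Visit 1 to Visit 4 "should be at least 28 days, but should not exceed 42 days" (Protocol Section 6.1); Visit 4 falls 14±2 days before Day 1 (Protocol Section 6.2).

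- The plan's own figure first: Section 6.1 gives a 56-day screening limit that includes the 14-day run-in. 42 + 14 = 56, so it reproduces. It also fits the stated total participation of about 19 weeks: (56 + 42 + 35)/7 = 19.0.
- From the visit windows, the shortest period is 28 + (14 − 2) = 40 days and the longest is 42 + (14 + 2) = 58 days.
- Section 6.1 also names 72 days as the maximum from Screen 1 to Day 1. The 56, 58 and 72 days should be reconciled, but on any of them AEs are collected for about six weeks or more before dosing. Only those still ongoing at Day 1 matter here.

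**2. Which events fall through.** An event is affected only if all four conditions hold:

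- it began after consent and before the first double-blind dose;
- it was still ongoing at Day 1;
- it then increased in severity or became serious;
- the site kept it as one record.

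The first condition makes it an earlier event under SAP Section 3.5, and Section 6.6 then lists it only. A single maximum grade does not show whether the peak came before or after Day 1, so the listing cannot resolve the question later.

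**3. How many subjects.** The documents give no rate for either step. Assumptions: share of subjects with an AE ongoing at Day 1, *a* = 0.10 to 0.30; share of those whose AE worsens on treatment and is kept as one record, *b* = 0.10 to 0.25. Expected number affected = *n* × *a* × *b*.

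- Share of subjects: 0.10 × 0.10 = 1.0% to 0.30 × 0.25 = 7.5%.
- 28-subject arm: 28 × 0.010 = 0.28 to 28 × 0.075 = 2.1.
- 14-subject placebo arm: 14 × 0.010 = 0.14 to 14 × 0.075 = 1.05.
- All 98 subjects: 98 × 0.010 = 0.98 to 98 × 0.075 = 7.35.
- Chance that a 28-subject arm has at least one such subject, 1 − (1 − *ab*)^28: about 25% at 1.0% and about 89% at 7.5%.

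**4. From undercount to bias.** These are absolute undercounts. If the worsening share is the same in every arm, each arm loses the same expected percentage and the expected difference between arms does not change. Bias in the comparison needs differential worsening, and nothing in the documents allows an estimate of it.

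**The case against.** The case against has real force on five points.

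- **The wording.** A reader might infer that the SAP counts an AE only if it starts after dosing, and so deliberately excludes worsening. The text does not go that far. It speaks of AEs occurring after the start of treatment, contains no explicit onset-date test, and does not mention worsening. This stands: the defect is a rule that is silent on one class of event, with a plain reading that leaves the class out.
- **The outside standard.** AE summaries also follow the sponsor's data standards, which are not in the documents and may contain a worsening rule. A reader might infer that worsened events are never counted by arm, but that cannot be known without those standards. This stands as a limit on certainty. It does not remove the need for the SAP to state or cite the rule.
- **The one-record assumption.** Protocol Section 8.3 applies only where the CRF requires severity, and it does not settle whether worsening opens a new record. Protocol Section 8.2.1 lists worsening of underlying disease as an AE in itself. A worsening entered as a new AE after dosing would be counted under the SAP as written. With about 30 sites and no instruction, practice may vary.
- **Other outputs.** Laboratory, vital-sign and ECG changes are summarized by treatment, and the two adverse drug reactions that Protocol Section 1.3.2 names for PF-05221304 (raised triglycerides, lowered platelets) are laboratory measures. SAEs are all reported, and discontinuations are counted by treatment. The gap is therefore mainly in symptomatic AEs.
- **The size.** A reader might infer distortions of up to 14 percentage points, since 2 of 14 placebo subjects is 14.3%. The assumptions above do not support that as an expected effect: their maximum is 7.5% of subjects, or 1.05 of 14.

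**Conclusion.** The point holds as a gap in the stated classification rule. On the plain reading of SAP Sections 3.5 and 6.6 together, an AE ongoing at Day 1 that worsens or becomes serious on drug and is kept as one record is listed but not tabulated by treatment. No other text in the protocol or SAP brings it back in.

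The expected size is small to moderate for arms of 14 and 28, ranging from well under one subject to about two per active arm. It rests wholly on the assumed 10-30% and 10-25%. The documents do not show that any such event would in fact go uncounted, because the sponsor's standards or site practice may capture it. Nor do they show that the comparison between arms would be biased, because that requires worsening to differ by arm. It is worth fixing because the endpoint is a stated secondary one and the remedy is cheap.

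**What to change.** In SAP Sections 3.5 and 6.6, define a treatment-emergent AE as any AE that starts, increases in severity, or becomes serious after the first double-blind dose. AEs that start before dosing and do not worsen stay listed only. If the sponsor's data standards already contain this rule, state it in the SAP in the same words.

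In the CRF completion guidelines, have sites record the date and grade of any worsening after Day 1, for example as a new AE record with its own start date. This must be in place while data are collected, because a single maximum grade cannot be split by time afterwards.

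The cost is one SAP sentence and one CRF instruction. The downside is slightly higher treatment-emergent AE counts.

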## Laboratory Data

Safety laboratory tests will be performed as described in the protocol.

To determine if there are any clinically significant laboratory abnormalities, the haematological, clinical chemistry (serum), and urinalysis safety tests will be assessed against the criteria specified in the sponsor reporting standards. The assessment will take into account whether each subject's Baseline test result is within or outside the laboratory reference range for the particular laboratory parameter.

Baseline is defined as the result closest *prior to* dosing on Day 1.

# Vital signs

Seated blood pressure and pulse rate measurements will be taken at time points detailed in the Schedule of Activities given in the protocol.

Baseline is defined as the result closest *prior to* dosing on Day 1. The following vital signs endpoints will be determined for each subject:

- The maximum decrease and increase from Baseline over all measurements taken postdose for systolic and diastolic blood pressures.
- The maximum increase and decrease from Baseline over all measurements taken postdose for pulse rate.

The maximum increase from Baseline will be calculated by first subtracting the Baseline value from each post-dose measurement to give the change from Baseline. The maximum of these values over the respective period will then be selected, except in the case where a subject does not show an increase. In such an instance, the minimum decrease should be taken. Similarly, the maximum decrease from Baseline will be determined by selecting the largest negative value of the changes from Baseline. In cases where a subject does not show a decrease, the minimum increase should be taken.

# ECGs

Single 12-lead ECGs will be obtained on all subjects at times detailed in the Schedule of Activities given in the protocol. Baseline is defined as the result closest *prior to* dosing on Day 1.

The QT, QTcF, heart rate, QRS and PR will be recorded at each assessment time. If not supplied, QTcF will be derived using Fridericia's heart rate correction formula:

 $QTcF = QT / (RR)^{1/3}$ , where RR = 60/HR (if RR is not provided)

The maximum absolute value (post-dose) and the maximum increase from Baseline for QTcF, heart rate, PR and QRS, will be determined among overall post-Baseline measurements for each subject.

The maximum increase from Baseline will be calculated by firstly subtracting the Baseline value from each post-dose measurement to give the change from Baseline. The maximum of these values over the respective period will then be selected, except in the case where a subject does not show an increase. In such an instance, the minimum decrease should be taken preserving the sign of change.

# Non-Standard Safety Assessments

Serum creatinine (Scr) and serum cystatin C will be collected as part of the safety panel. From Scr estimated glomerular filtration rate (eGFR) will be calculated, if not supplied, using the modification of diet in renal disease (MDRD) equation.

MDRD Formula: GFR (mL/min/1.73 m^2) = 175 × (Scr)-1.154 × (Age)-0.203 × (0.742 if female) × (1.212 if black)

GFR will be estimated from the cystatin C using the CKD-Epi-Cystatin C equation:

• For serum cystatin C (Scys)  $\leq 0.8$  mg/L:

eGFR (mL/min/1.73 m^2) =  $133 \times (Scys/0.8)^{-0.499} \times 0.996^{Age} \times 0.932$  if female]

• For serum cystatin C (Scys) >0.8 mg/L:

eGFR (mL/min/1.73 m^2) =  $133 \times (Scys/0.8)^{-1.328} \times 0.996^{Age} \times 0.932$  if female]

Baseline is defined as the result closest *prior to* dosing on Day 1.

	Page 12	
CCI		

# 4. ANALYSIS SETS

Data for all subjects will be assessed to determine if subjects meet the criteria for inclusion in each analysis population prior to unblinding and releasing the database and classifications will be documented per standard operating procedures.

#### 4.1. Full Analysis Set

The Full Analysis Set (FAS) is defined as *all randomized subjects who received at least one dose of IP*; subjects are assigned to the randomized treatment regardless of what treatment was received. This is the primary analysis population for all efficacy analyses.

#### 4.2. Per Protocol Analysis Set

This will not be used in the current study.

#### 4.3. Safety Analysis Set

All subjects who receive at least one dose of IP post-randomization will be included in the safety analyses and listings. All safety endpoints will be analyzed by the treatment that the subjects actually receive (for the majority of the study duration) regardless of which treatment group they are randomized. A randomized but not treated subject will be excluded from the safety analyses. A treated but not randomized subject will be reported under the treatment actually received.

## 4.4. Other Analysis Sets

*Pharmacogenomic and biomarker data will be collected and retained for future analyses, but will not be analyzed for the purposes of CSR.* 

# 5. GENERAL METHODOLOGY AND CONVENTIONS

The analysis will be performed after database release, following last subject last visit.

## 5.1. Hypotheses and Decision Rules

The following null hypotheses will be tested for the primary endpoint:

- 1. The PF-05221304 + PF-06865571 combination is equal in effect to placebo.
- 2. The PF-05221304 monotherapy is equal in effect to placebo.
- 3. The PF-06865571 monotherapy is equal in effect to placebo.
- 4. The PF-05221304 + PF-06865571 combination is equal in effect to the PF-05221304 monotherapy.
- 5. The PF-05221304 + PF-06865571 combination is equal in effect to the PF-06865571 monotherapy.

The alternative hypotheses corresponding to the above null hypotheses will be the following 2-sided hypotheses:

- 1. The PF-05221304 + PF-06865571 combination is different from the effect of placebo.
- 2. The PF-05221304 monotherapy is different from the effect of placebo.
- 3. The PF-06865571 monotherapy is different from the effect of placebo.
- 4. The PF-05221304 + PF-06865571 combination is different from the effect of the PF-05221304 monotherapy.
- 5. The PF-05221304 + PF-06865571 combination is different from the effect of the PF-06865571 monotherapy.

The following confidence intervals (CIs) associated with the above hypotheses will be constructed:

- 1. 2-sided 90% CI
- 2. 2-sided 90% CI
- 3. 2-sided 90% CI
- 4. 2-sided 90% CI and 2-sided 50% CI
- 5. 2-sided 90% CI and 2-sided 50% CI

#### No adjustment for multiple comparisons will be made.

Interim analyses (IAs) may be performed for safety or efficacy (see Section 7 for further detail). IA results may be used for internal business decisions regarding future study planning or stopping for futility. As such no adjustment in the Type I error rate is proposed.

## 5.2. General Methods

## **Descriptive Statistics**

Descriptive statistics, including the sample size, mean, standard deviation (STD), median, minimum (min), and maximum (max) values, will be provided for continuous endpoints. Some measures will be summarized using graphical representations by treatment and study day of visit, where appropriate.

## Mixed Model for Repeated Measurements (MMRM)

This model will be used for the analysis of endpoints with more than one post-Baseline collection time point. All observed data collected during the post-Baseline treatment period will be utilized. The MMRM analysis will be performed with treatment, study day and treatment-by-study day interaction as fixed effects, Baseline value of the analysis endpoint, and Baseline whole liver PDFF. If the endpoint being analyzed is log-tranformed, the Baseline value of the analysis endpoint and the Baseline whole liver PDFF will also be log-transformed. Repeated measures model with unstructured correlation matrix will be utilized. If this does not converge then compound symmetry structure will be considered. Additionally, the number of covariates may be reduced to improve model fit. Estimates of

treatment effects will be assessed using least square means (LSMs) and CIs at each time point. LSM difference for each comparison along with the CIs and 2-sided p-values will be provided. If there are major deviations from the statistical assumptions underlying this model then alternative transformations (eg, log) or non-parametric analyses may be presented. Justification for any alternative to the planned analysis will be given in the study report.

## Analysis of Covariance

The ANCOVA model will be used with continuous endpoints for landmark (single time point) analyses. The model will include treatment group as fixed effect, Baseline value of the endpoint being analyzed, Baseline whole liver PDFF as covariates. Diabetes status will be included as a covariate for the primary endpoint only if at least 1/3 of the subjects have T2DM. If the endpoint being analyzed is log-tranformed, the Baseline value of the analysis endpoint and the Baseline whole liver PDFF will also be log-transformed. Estimates of treatment effects will be assessed using LSMs and CIs. Estimates of the mean differences for each comparison and the corresponding CI will be obtained from the model. If there are major deviations from the statistical assumptions underlying this model then alternative transformations (eg, log) or non-parametric analyses may be presented. Justification for any alternative to the planned analysis will be given in the study report.

# Non-parametric Analysis

If the data have many outliers even after the log-transformation the following non-parametric analysis will be performed instead of the linear model. An outlier will be defined as any datapoint falling outside of 3.5x STD  $\pm$  the median. Additional evaluative statistics will be conducted to explore the nature of the outliers in order to determine the appropriateness of a parametric analysis.

For group medians, 90% CIs will be presented. In addition the CIs (see Section 5.1) will also be presented for differences in group medians from placebo group median. The method of McGill, Tukey, and Larson will be employed to calculate the CI for the difference in treatment group medians.

## 5.3. Methods to Manage Missing Data

In case of continuous endpoints, all available data will be utilized in the MMRM. The MMRM will provide unbiased estimates in case of missing at random (MAR). For the analysis of safety endpoints, the sponsor data standard rules for imputation will be applied. In case of biomarkers if the concentrations are above the upper limits of quantification such values will be truncated at the upper limit of quantification in all summary tables. If the concentrations are below the lower limits of quantification (LLQ) such values will be imputed by 0.5\*LLQ. However, in listings they will appear as reported.

	Page 15	
CCI		

In all pharmacokinetic data presentations (except listings), concentrations below the limit of quantification (BLQ) will be set to zero. (In listings BLQ values will be reported as "<LLQ", where "LLQ" will be replaced with the value for the LLQ.)

In summary tables and plots of the median values at each time point, statistics will be calculated having set concentrations to missing if one of the following cases is true:

- 1. A concentration has been collected as ND (ie, not done) or NS (ie, no sample),
- 2. A deviation in sampling time is of sufficient concern or a concentration has been flagged anomalous by the pharmacokineticist.

Note that summary statistics will not be presented at a particular time point if more than 50% of the data are missing.

